#### Discontinuation toxicities

1. Receives less than 80% of study treatments due to a toxicity related to NSCs or irinotecan, except CNS toxicities that are present at baseline and attributable to the location of the tumor or the neurosurgery.

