## Overall Treatment Plan

---

The following is an overview of the treatment plan:

1. Treatment cycles are defined by Day 1 study agent administration, except for Cycle 1 where Day 1 is defined as day of surgery. After Cycle 1, Day 1 agent administration will be NSCs, or for participants who are no longer receiving NSCs, Day 1 agent administration can be irinotecan.
2. Cycles are planned to be 28 days in duration, however the cycle may be extended for any of the following reasons:
  - a. A delay in administering the Day 1 treatment, resulting in an extension of the prior cycle.
  - b. A delay in administering the mid-cycle (Day 3, 15, 17) administrations, resulting in an extension of the respective cycle.
  - c. Dose level 1 or -1 participants will complete NSC treatment during cycle 1, and will start cycle 2 with irinotecan administration. As such, cycle 1 will be extended as needed (e.g. from 28 days to 30 days) to ensure that the cycle 2 day 1 irinotecan dose occurs 14 days after the previous irinotecan dose.
3. All safety assessments and immunology and RCR testing must be performed prior to administration of any study medication, and per the windows defined in Section 10. For planned assessments outside of schedule, written approval must be granted by the Principal Investigator.
4. Start of cycle criteria must be met in order to begin the treatment cycle. See Section 7.2.2.
5. Prior to administering any study agent at any time point, criteria for holding or modification of dose must be reviewed. See Section 7.2.4.
6. Adjustments to the schedule following a hold in study agent(s) are described in Section 7.3.
7. There will be no intra-patient dose escalation of NSCs or irinotecan.
8. Participants who discontinue irinotecan will discontinue all study treatment.
9. If administration of agents must be interrupted, dose reduced or terminated because of unacceptable toxicity or issues with the Rickham catheter, agent dosing will be modified according to rules described in Section 7. All changes to study agent administration must be recorded.
10. Prior to commencing treatment with NSCs, participants must have confirmed recurrent high grade glioma based on tumor taken during the Day 1 neurosurgery (Section 8.1). If recurrent high grade glioma is not confirmed, participants will be removed from therapy and replaced.

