#### Nervous system disorders

5. Grade 3 CNS disorder lasting > 7 days that is not present at baseline and is not attributable to the location of the tumor or the neurosurgery.
6. Second occurrence of a grade 3 CNS disorder that is not present at baseline and is not attributable to the location of the tumor or the neurosurgery.
7. Any grade 4 CNS disorder that is not present at baseline and is not attributable to the location of the tumor or the neurosurgery.

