#### **Criteria for Removal from Participation or Treatment**

---

For participants who begin treatment, duration of therapy will depend on individual response, evidence of disease progression and tolerance. In the absence of treatment delays due to adverse events, treatment may begin and continue until or unless one of the following criteria applies:

- Pathology review of the frozen section obtained at the time of surgery does not confirm recurrent high grade glioma (Section 8.1). Such participants will not continue on to receive any study agents, and all study procedures will end.

- Participant does not meet the criteria for initiating irinotecan dosing following surgery (Section 7.2.3). During cycle 1, if a participant requires more than 16 mg/day of dexamethasone to control cerebral edema at the time s/he is ready to begin treatment with irinotecan, then s/he will be considered neurologically unstable and will not continue with study treatment; however, the patient will still be evaluable for toxicity.
- Evidence of disease progression.
- Unacceptable adverse event(s) (see Section 7.2).
- Intercurrent illness that prevents further administration of treatment.
- Participant needs a treatment not allowed by the protocol.
- A participant may always be removed from treatment whenever s/he wishes.
- General or specific changes in the participant's condition render the participant unacceptable for further treatment in the opinion of the treating investigator.

Participants will be removed from study treatment when any one of the criteria listed above applies. The reason for study treatment removal and the date the participant was removed must be documented. Alternative care options will be discussed with the participant.

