**NOTE: See Section 6.1 for required and recommended prophylaxis and management.**

#### 7.1.1 Neurosurgery Toxicities

---

Bleeding, infection, headache, seizures, cerebral edema, pain, changes in neurologic function, thromboembolism.

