### 7.1.5 General Information

---

1. The study will use the NCI Common Terminology Criteria for Adverse Events (CTCAE) version 4.0 to grade toxicities. A copy of the version 4.0 can be downloaded from:  
<http://evs.nci.nih.gov/ftp1/CTCAE/About.html>
2. Whenever treatment is held pending resolution of toxicity to grade 1 or return to baseline, this criterion may also be met if the toxicity resolves to within 1 grade of the baseline value for a pre-existing laboratory abnormality. Baseline values are from screening assessments.
3. Study agents are always held together, regardless of the attribution of the toxicity.
4. NSC or irinotecan dose re-escalation is never permitted in this study.
5. If, for the best interest of the patient, the investigator wants to hold the study agent(s) or dose reduce (including increasing the dose reduction) after an adverse event in a manner not outlined in Table 7.2.4, this is permissible following discussion with and written approval the Principal investigator.\*
6. For situations where a participant experiences a toxicity which the treating investigator feels is unlikely related to treatment with either study agent, but which requires hold or reduction of either agent according to Table 7.2.4, maintaining treatment or maintaining treatment dose is allowable per discussion with and written approval by the Principal Investigator.\*
7. For holds due to toxicities related to study agent(s), if the participant does not meet criteria to resume treatment within 28 days of their last NSC administration (or irinotecan for Dose Level 1/1 participants after they have completed cycle 1), the participant must permanently discontinue study treatment (both agents). However, if the participant is clearly benefiting from the study, the investigator may contact the Principal Investigator to determine if the participant can remain on study and at what dose level. Agreement of the Principal Investigator is to be documented in writing.\*
8. For holds for reasons other than treatment related toxicities, such as inclement weather or adverse events unrelated to study agents, if the participant does not meet criteria to resume treatment within 28 days of their last NSC administration, the study agent(s) may be restarted with written approval from the Principal Investigator, as long as there has been no significant evidence of disease progression during the treatment interruption.\*

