- b. To be performed within 14 days from planned date of surgery, except for MRI (footnote ee) to be performed within 28 days of registration.
- c. Laboratory evaluations to be performed and results reviewed within 2 days prior to agent administration. Laboratory evaluations may be performed at a clinic local to the participant.
- d. 'Start of Cycle' criteria are found in Section 7.2.2. All assessments to occur prior to administration of NSCs (or irinotecan for dose levels 1/-1).
- e. All assessments to occur prior to administration of NSCs (or irinotecan for dose levels 1/-1).
- f. Imaging (brain MRI and PET/CT scans) should at least be done at the end of every 2 cycles (Day 28 -3days).Imaging can be done more frequently than after every 2 cycles to closely follow up on changes of unknown significance seen on a prior brain MRI or PET/CT scan.
- g. End of treatment assessments to be performed within 7 days after last study agent administration or within 7 days after decision to end treatment. Assessments may continue for ongoing reportable adverse events or events resulting in a dose modification.
- h. A contact/visit for review of adverse events, KPS, concomitant medication review, and vital status is to be performed at 30 days +/- 2 days after the last study agent is given. This may be performed via documented phone conversation with a study nurse or clinician. All participants will be followed until resolution or stabilization of any serious or reportable adverse events occurring during treatment or starting within 30 days of last study agent.
- i. Long-term follow-up to occur until death for updated medical history, RCR testing, and tissue at autopsy. Required elements occur at 3 months (+/-14 days), 6 months (+/-14 days) and annually from start of study treatment, and upon patient death. See footnotes z, rr, and ss for details.
- j. Performed by MD attending only. Informed consent process to be fully documented.
- k. Background/medical history – to include review of treatment history for glioma, any ongoing medical conditions and medical history pertaining to eligibility on study and involvement during study.

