- v. For immunological correlative studies: notify CICSL by e-mail to [[contact]](mailto:[contact]) at least 24 hours in advance of sampling. Collect six 6-ml lavender top (K-EDTA) tubes, keep on wet ice, and send to COH CICSL; collect approximately 10 ml of blood in red top tubes, keep upright at room temperature and process as per Section 8.6.1 before sending to the COH CICSL and Clinical Pathology. On days where study agent is administered, samples are always to be taken prior to agent administration.
- w. If participant is removed (or withdraws) from the trial prior to receiving study agent, the samples are to be discarded.
- x. Cycle 2 only.
- y. For RCR testing, collect two 6-ml lavender top (K-EDTA) tubes (or a volume of 10ml) maintained at room temperature with gentle agitation ~hourly and send to CICSL. On days where study agent is administered, samples are always to be taken prior to agent administration. Notify CICSL by e-mail to [[contact]](mailto:[contact]) in advance of sampling.
- z. RCR testing is required for all patients at 3 months\* and 6 months\* and annually\* thereafter post start of study treatment, whether patient is on treatment or in long term follow-up. For patients still on treatment, assuming there are no delays in treatment, this means RCR testing is to be performed at C4D1 and C7D1. Take RCR testing at most appropriate clinic visit for patients still on study treatment. For patients in long term follow-up, samples may be obtained via local physician and shipped to COH for testing. (\*+/-14 days)
- aa. CBC with ANC: hemoglobin, hematocrit, platelets, total WBC and neutrophils
- bb. Comprehensive metabolic panel: Sodium, potassium, chloride, carbon dioxide, creatinine, urea nitrogen, calcium, glucose, albumin, total bilirubin, alkaline phosphatase, total protein, ALG/SGPT and AST/SGOT.
- cc. Serum pregnancy test only for women of child bearing potential.
- dd. A contrast, non-contrast MRI is to be performed for screening within 28 days from registration. (Day 2 post-surgical MRI will serve as the baseline MRI).
- ee. A pre-surgical planning post-registration MRI **may** be performed if indicated by the neuro-surgeon.
- ff. A contrast, non-contrast MRI will be performed for all patients at least every two months.
- gg. A PET/CT scan will be performed within 7 days after surgery to serve as the baseline scan, and then a PET/CT scan will be performed whenever possible at the time follow up brain MRIs are done.

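### The DLT definition words the CNS exemption in two conflicting ways and does not say whether NSC injection belongs to the neurosurgery

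*Combined protocol and SAP*

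**What the plan says.** Section numbers follow the protocol's own cross-references; the DLT definition is 5.3.3, although its heading in the body text is numbered 5.1.3.

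A DLT must (a) be at least possibly related to NSCs, irinotecan or the combination, (b) occur in cycle 1, and (c) meet any one of a list of criteria. Two parts of that list contain a CNS exemption.

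- Item 1 counts a patient whose agent-related toxicity leaves under 80% of study treatment received. It has no grade threshold. Its exemption is worded "except CNS toxicities that are present at baseline and attributable to the location of the tumor or the neurosurgery".
- Items 5 to 7 count certain grade 3 and 4 CNS disorders. Item 7 reads "Any grade 4 CNS disorder that is not present at baseline and is not attributable to the location of the tumor or the neurosurgery"; items 5 and 6 use the same exclusion.

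Section 5.3.3 defines neither baseline nor the neurosurgery. Elsewhere:

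- Section 7.2.1, on treatment holds: "Baseline values are from screening assessments". Table 10 footnote b times screening: "To be performed within 14 days from planned date of surgery".
- Table 10 footnote dd, for imaging only: "Day 2 post-surgical MRI will serve as the baseline MRI".
- Section 5.1 item 10 uses the term for the operation itself: "tumor taken during the Day 1 neurosurgery". Table 10 footnote jj is wider: neurosurgery there may include catheter placement and NSC administration.
- Table 7.2.4 repeats the surgical exclusion for dose modification, without a baseline condition and without a rule for an event attributed to both surgery and NSCs.

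**The concern.** The first NSC dose is normally given during the operation, so a new CNS event in the first days may reasonably be attributed to the surgery and also rated possibly related to the cells. That is the event on which the two wordings disagree. If dosing stops, a monitoring team that reads item 1 literally records a DLT. A team that applies the exemption as items 5 to 7 word it records none and replaces the patient.

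The second gap runs the other way. If the team takes the meaning of neurosurgery from footnote jj, a grade 3 or 4 deficit caused by the injection could be excluded under items 5 to 7, although limb (a) is meant to capture toxicity from giving the NSCs.

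At stake is the DLT count, the primary result, which rests on 3 to 6 patients per level. The DLT rate reported with Clopper-Pearson limits and the 34% review trigger in the expansion cohort use the same definition.

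**Working it through.** **The plan's own figures.** Section 15.1 gives detection probabilities that depend on what is counted as a DLT. They reproduce: 1 − 0.75^6 = 0.822 (stated 82%) and 1 − 0.85^14 = 0.897 (stated 90%). The maximum Clopper-Pearson half-widths are 0.382 and 0.270 (stated 0.38 and 0.27). None of these is in dispute.

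**The two wordings side by side.** Let A be present at baseline, and B be attributable to the tumor location or the neurosurgery. Item 1 exempts A and B. Items 5 to 7 count a disorder only when neither A nor B holds, so they exempt A or B.

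| A | B | Exempt, item 1 | Exempt, items 5–7 |
|---|---|---|---|
| no | no | no | no |
| no | yes | no | yes |
| yes | no | no | yes |
| yes | yes | yes | yes |

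They disagree in 2 of 4 cells. The second row is the new, surgery-attributed event. Because meeting one criterion is enough, item 1 prevails when dosing has stopped.

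**A concrete case.** A patient receives NSCs on Day 1, develops new cerebral edema, and on Day 3 "requires more than 16 mg/day of dexamethasone to control cerebral edema". Section 5.5 ends study treatment but keeps the patient evaluable for toxicity.

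- Doses received at levels 2 to 4: 1 of (2 NSC + 2 irinotecan) = 25%. At level 1: 1 of (1 + 2) = 33%. Both are below 80%.
- Section 7.1.1 lists the neurosurgery toxicities: "Bleeding, infection, headache, seizures, cerebral edema, pain, changes in neurologic function, thromboembolism". Attribution to the surgery is therefore natural.
- If NSCs are also rated possible, limb (a) is met. Item 1 read literally then makes this a DLT at any grade. Items 5 to 7 would exempt the same cause.
- If the event is treated as exempt, the patient has neither a DLT nor 80% of each agent, and Section 5.3.2 has the patient replaced.

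**What one such patient does.** Let p be the rate of other, undisputed DLTs (assumed). Level 4 is accepted with at most 1 DLT in 6.

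- Replaced: six other patients, (1 − p)^6 + 6p(1 − p)^5.
- Counted: the remaining five must have none, (1 − p)^5.

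| p | Replaced | Counted |
|---|---|---|
| 0.05 | 0.735 + 0.232 = 0.967 | 0.774 |
| 0.10 | 0.531 + 0.354 = 0.886 | 0.590 |
| 0.15 | 0.377 + 0.399 = 0.776 | 0.444 |

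At level 1, 2 or 3, with the patient among the first three and p = 0.10, the chance of escalating is (1 − p)^3 + 3p(1 − p)^5 = 0.729 + 0.177 = 0.906 if replaced, against (1 − p)^5 = 0.590 if counted.

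**The case against.** **Cause is already tested.** Limb (a) and item 1's own words both require a relation to NSCs or irinotecan, and Section 7.2.4 leaves attribution to the investigator. This stands. A reader might infer that item 1 turns purely surgical deficits into DLTs; it does not. An event not even possibly related to either agent is not a DLT on any reading.

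**Item 1's surgical exemption is not empty.** Screening precedes the operation, so a reader might infer that the exemption can never apply to an effect of the Day 1 surgery. But Section 11.3 counts a change in an existing condition as an adverse event, and a screening deficit worsened by the operation can meet both conditions. The difficulty is confined to new events. The screening baseline is itself an inference, since Section 7.2.1 states it for treatment holds and not for DLTs.

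**Item 1 can be read loosely** as exempting baseline events and, separately, attributable ones, which would match items 5 to 7. That is possible, but a rule that decides escalation should not depend on which reading the team adopts.

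**A grade 4 event on Day 1 would usually end dosing too**, because Day 3 irinotecan requires good post-operative recovery, so item 1 would govern it as well. Agreed. It means that the conflict mostly arises within one patient who meets both sets of items, and that item 1 then overrides the wider exemption.

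**Counting a treatment-ending, possibly NSC-related event is defensible caution in phase I.** It is, if chosen. The plan instead writes a surgical exemption into item 1 and then words it more narrowly than in items 5 to 7, without saying why.

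**The probabilities show what any additional DLT does in a 3+3 design.** This is correct, and they are offered only as that.

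**Conclusion.** The concern holds for a limited class of events: new peri-operative CNS events attributed to the surgery and also rated at least possibly related to NSCs. For these, item 1 and items 5 to 7 give opposite answers once dosing falls below 80%. Independently, footnote jj leaves open a reading under which items 5 to 7 exempt a CNS event caused by the injection.

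Given one patient on whom the readings differ at level 4, acceptance of that level is 89% if the patient is replaced and 59% if counted, at an assumed agent DLT rate of 10%. The pairs are 97% and 77% at 5%, and 78% and 44% at 15%. These figures assume independent patients with a common DLT rate and are conditional on the event happening. A reader might go on to infer a loss for the trial as a whole. The documents give no frequency for such events, so that cannot be supported.

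The text should be corrected before escalation decisions are made under it: the edit is small and the rule determines the primary endpoint.

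**What to change.** Two edits to Section 5.3.3.

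1. In item 1, replace the *and* between the baseline condition and the attribution condition with *or*, so that the exemption matches items 5 to 7.
2. Add: *For DLT assessment, baseline is the screening neurological exam; the neurosurgery means the resection or biopsy and excludes NSC injection, notwithstanding Table 10 footnote jj.*

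How to class an event attributed to both the surgery and the NSC injection remains the sponsor's choice, provided that the same rule applies to item 1 and items 5 to 7. One option is to deny the exemption whenever a relation to NSC injection is possible. It has a drawback: limb (a) already requires at least a possible relation, and no irinotecan has been given before Day 3, so the surgical exemption would have nothing left to do for Day 1 and 2 events, and edit 1 would be largely cancelled for them.

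The cost is a one-word change and one sentence, with no new data, visits or staff. The downside is that some events that end dosing and are attributed to the surgery, which are DLTs under a literal item 1 today, would become exempt.

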#### Hematological toxicities

1. Grade 4 thrombocytopenia
2. Grade 4 neutropenia lasting > 7 days
3. Grade 4 anemia
4. Febrile neutropenia if ANC <  $0.5 \times 10^9/L$

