**Study Design:**

This phase I clinical trial will define the recommended phase II dosing (RP2D) based on dose-limiting toxicities (DLTs) and the full toxicity profile of the combination of hCE1m6-NSCs and irinotecan using a standard "3 + 3" dose escalation schema in patients with recurrent highgrade gliomas who are undergoing a debulking craniotomy or stereotactic brain biopsy. Except for dose levels 1 and -1, where only 1 dose of NSCs will be given (these patients can continue to receive treatment with irinotecan every 2 weeks), NSCs will be administered intracranially on days 1 and 15, and irinotecan will be given intravenously 2 days later, on days 3 and 17 of a 28 day cycle. With subsequent cohorts of patients, the NSC dose will be increased as tolerated, but the dose of irinotecan will remain the same unless DLTs occur that necessitate lowering the dose of irinotecan. A Rickham reservoir/catheter system will be placed at the time of surgery for delivering repeat doses of NSCs intracranially. MRIs and PET/CT scans of the brain will be performed at least every two months (at the end of every even cycle of study treatment to evaluate response).

Three doses of NSCs will be assessed. The starting dose will be  $5 \times 10^7$  NSCs, which was well-tolerated in the first-in-human study of CD-expressing NSCs. Due to volume limitations for intracerebral administration, the highest dose of NSCs to be tested will be  $1.5 \times 10^8$  cells. Study participants will receive repeat cycles of study treatment (dose level 1 and -1 patients will only receive repeat doses of irinotecan) as long as they are tolerating the treatment well, and there is no evidence of progressive disease.

An important secondary objective of this study will be to determine the biologic activity of the hCE1m6-NSCs by measuring concentrations of SN-38 in brain interstitium using intracerebral microdialysis. The first 6 patients to enroll in the study and the last 8 patients in the expansion cohort will undergo microdialysis to collect data regarding intracerebral levels of irinotecan and SN-38 when patients are treated with the lowest and highest NSC doses. Please note, the same dose of NSCs ( $5 \times 10^7$ ) is given to patients on dose levels 1 and 2, so whether the first 6 patients are all treated on dose level 1 or the first 3 dose level 1 and the next 3 on dose level 2, they will all receive the same dose of NSCs.

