**A DLT is defined as an adverse event that:**

- (a) is related to the administration of NSCs, irinotecan or the combination of NSCs with irinotecan, with an attribution of possible, probable, or definite, and
- (b) occurs during the first treatment cycle (including Cycle 2 Day 1 safety assessments), and
- (c) meets any of the following criteria:

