##### **Common:**

Neutropenia and/or late diarrhea (occurring more than 8 hours after irinotecan administration) are common dose-modifying toxicities.

Other commonly observed adverse events include nausea and vomiting, anorexia, weight loss, abdominal cramping, constipation, alopecia, asthenia, lymphocytopenia, anemia, fever, and dehydration as a result of diarrhea and/or vomiting.

Patients may experience an acute syndrome of lacrimation, diaphoresis, vasodilation (flushing), abdominal cramping, and diarrhea (early diarrhea) during or shortly after irinotecan administration; this syndrome is thought to be cholinergically mediated.

**Less common:** mucositis, colitis (sometimes with gastrointestinal bleeding), skin irritation at infusion site, headache, dizziness, confusion, somnolence, flatulence, dyspepsia, rash, minor infection

**Rare, but serious:** pulmonary toxicity (manifested as shortness of breath, non-productive cough, and transient infiltrates on chest x-ray), elevated hepatic enzymes, increased serum creatinine, thrombocytopenia, infusion reaction, neutropenic infection, febrile neutropenia

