**Table 10 Study Activity Calendar**

	Screening b	Cycle 1 a										Cycle 2+					End of Tx g	30-Day Post Tx h	Long Term Follow-Up, Autopsy i
		Day 1	Day 2	Day 3	Day 4	Day 5	Day 8	Day 10	Day 15	Day 17	Day 22	Day 1c,d	Day 3	Day 15 e	Day 17	Day 28 f			
Informed consent j	X																		
Background/medical history k	X																		
Inclusion/Exclusion criteria l	X																		
Histology confirmation	X m	X n																	
Vitals, KPS, neuro & physical exams o	X		X	X							X p			X		X	X	X q	
Adverse event assessment r	X		X	X			X			X p		X	X		X		X	X	
Concomitant meds review s	X		X	X					X p			X		X			X	X	
HLA antibody screening u	X																		
UGT1A1 polymorphism v	X																		
Immunological studies w	X x								X p			X y		X			X		
RCR testing z	X x																		
Coagulation: PT/INR, PTT	X																		
CBC with ANC aa	X			X			X		X p			X c		X c			X		
Comprehensive Metabolic Panel bb	X			X				X p			X c						X		
Serum Pregnancy Test cc	X																		
Chest X-ray and EKG	X																		
Imaging – MRI	X dd	X ee	X ff													X ff	X hh		
Imaging – PET/CT scan of the brain		X gg														X gg	X hh		
Response Assessment ii																X	X ii		
Neurosurgery		X jj			X kk														
Administration of hCE1m6 - NSCs		X ll							X m			X m		X m					
Non-contrast Brain CT		X																	
Dialysate, blood pK collection oo			X	X	X														
IV administration of irinotecan pp			X rr						X			X ss	X tt	X ss	X tt				
Post-Study Tx Medical History uu																		X	
Tissue from autopsy vv																			X

- a. For patients on dose level 1 /-1, Cycle 1 will be a minimum of 30 days to ensure that 14 days have passed between irinotecan doses.

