- l. Inclusion/exclusion criteria. Source documentation providing investigator's confirmation that patient has met all eligibility criteria must be available prior to registration. In addition, source documentation by neurosurgeon that (a) a physical connection between the post-resection tumor cavity and cerebral ventricles is not anticipated, (b) a gross total resection is not anticipated, (c) the prospective participant is able to undergo neurosurgery, and (d) documentation that patient "needs a biopsy/craniotomy" is needed.
- m. Histology confirmation for to be performed by COH pathologist.
- n. Real-time histology confirmation to occur during surgery on fresh frozen section. See section 8.1 for pathology criteria. If confirmation of high grade glioma not obtained, all further study procedures will cease.
- o. Vital signs: Weight, heart rate, blood pressure, respiration rate, temp. Height required only at baseline. KPS not required at Day 2 and 3. See Appendix A for KPS scale.
- p. Participants no longer receiving NSCs (e.g. Dose Levels 1 and -1) may have their Day 15 assessments performed on Day 17, prior to irinotecan dosing.

- q. KPS and vital status only. Vital signs and Neuro-Physical exam are not required.
- r. Adverse events experienced by participants will be collected and recorded from signing of informed consent document up to 30 days of the last dose of study medication. The period for collection and recording of AEs is extended for participants with ongoing “reportable” adverse events that are related to study agent. Adverse event reporting begins for events that occur on Day 1 (day of neurosurgery).
- s. The only concomitant medication that needs to be documented in the case report form is whether the patient is taking dexamethasone (or another corticosteroid), and if so, what the dose is.
- t. For HLA testing, collect blood in 1 red top tube. Maintain at room temperature. Bring samples to COH Histocompatibility Laboratory.
- u. Participants who have already undergone UGT1A1 genotyping may use those results and do not the procedure repeated.

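### Table 10 appears to schedule no blood count after the Day 17 irinotecan dose until the Cycle 2 Day 1 labs, so some cycle 1 hematologic DLTs may be under-counted, which would favour escalation

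*Combined protocol and SAP*

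**What the plan says.** Irinotecan timing: the synopsis (Study Design) states that "irinotecan will be given intravenously 2 days later, on days 3 and 17 of a 28 day cycle".

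DLT window: the definition of DLT requires that the event "occurs during the first treatment cycle (including Cycle 2 Day 1 safety assessments), and" that it meets a listed criterion. The hematologic criteria are grade 4 thrombocytopenia, "Grade 4 neutropenia lasting > 7 days", grade 4 anemia, and febrile neutropenia with ANC below 0.5 × 10⁹/L. Only the neutropenia criterion carries a duration.

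Expected toxicity: the irinotecan toxicity section says "Neutropenia and/or late diarrhea (occurring more than 8 hours after irinotecan administration) are common dose-modifying toxicities".

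Scheduled counts: in Table 10 the row "CBC with ANC aa" is marked at Screening, cycle 1 Days 3, 8 and 15 (footnote p), Cycle 2+ Days 1 and 15 (footnote c), and End of Treatment. The Day 17 and Day 22 columns exist but are blank in this row.

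Footnotes: footnote c reads "Laboratory evaluations to be performed and results reviewed within 2 days prior to agent administration" and adds "Laboratory evaluations may be performed at a clinic local to the participant". Under footnote p, participants no longer receiving NSCs "may have their Day 15 assessments performed on Day 17, prior to irinotecan dosing". Footnote a gives dose levels 1 and -1 a first cycle of at least 30 days.

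Unscheduled counts: Section 10 permits procedures to become more frequent when clinically indicated or after a toxicity. It does not require this.

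**The concern.** DLTs in cycle 1 are the primary endpoint for dose escalation. Half of the planned cycle 1 irinotecan is given on Day 17, and neutropenia is an expected effect of that drug. If the next scheduled count is at the very end of the DLT window, a nadir that has already recovered leaves no trace. A single low value at that point also cannot show how long the episode lasted.

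Under the 3+3 rules one unseen event can change a decision: a true 2/6 (MTD exceeded) is scored as 1/6 (escalate). Where DLTs are attributed only to irinotecan, the plan de-escalates only the irinotecan schedule, so a missed event could leave that schedule in place. An unseen nadir is also a safety matter for the patient.

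**Working it through.** **1. The calendar row.** Table 10 has 19 columns after the row label: Screening; cycle 1 Days 1, 2, 3, 4, 5, 8, 10, 15, 17, 22; Cycle 2+ Days 1, 3, 15, 17, 28; End of Treatment; 30-day; long-term follow-up. The CBC marks fall in columns 1, 4, 7, 9, 12, 14 and 17. Footnote p (a Day 15 note) falls on Day 15, and footnote c falls on Cycle 2+ Days 1 and 15. No mark is left over for Day 22.

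**2. The gap.** Cycle 2 Day 1 is Day 29, or Day 31 at levels 1 and -1. Footnote c lets the labs come up to 2 days early.
- Other levels: labs on Days 27–29, which is 27 − 17 = 10 to 29 − 17 = 12 days after irinotecan.
- Levels 1 and -1: labs on Days 29–31, which is 12 to 14 days after.

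**3. Which neutropenia DLTs are missed entirely.** Take a grade 4 episode of L full days starting on Day d ≥ 18. It is unseen if its last day, d + L − 1, falls before the count.

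| Count on | L = 8 | L = 9 | L = 10 | L = 11 | L = 12 | L = 13 |
|---|---|---|---|---|---|---|
| Day 27 | d 18–19 | d 18 | none | none | none | none |
| Day 29 | d 18–21 | d 18–20 | d 18–19 | d 18 | none | none |
| Day 31 (levels 1, -1) | d 18–23 | d 18–22 | d 18–21 | d 18–20 | d 18–19 | d 18 |

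Grade 4 thrombocytopenia or anemia needs no minimum duration, so any episode that starts after Day 17 and recovers before the count is missed by the schedule.

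**4. Duration.** No two scheduled counts lie between Day 17 and the end of the window. In the first half of the cycle, Days 8 and 15 are 15 − 8 = 7 days apart, so two grade 4 values document 7 elapsed days, not more than 7. (Counting both dates would give 8; the plan does not say how to count.) A Day 22 count would give 29 − 22 = 7 days again, or 5 to 6 if the Cycle 2 labs are drawn early. The general window of 3 days either way in Section 10 leaves these intervals uncontrolled.

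**5. Effect on decisions.** First, the plan's own figures in Sample Size: the chance of at least one event is 1 − (1 − p)ⁿ. For n = 6, p = 0.25 it is 0.822 (stated: about 82%). For n = 14, p = 0.15 it is 0.897 (stated: about 90%). Both reproduce.

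The chance of escalating from a level is (1 − p)³ + 3p(1 − p)⁵. If a share m of all DLTs is missed, p becomes p(1 − m). The documents give neither p nor m, so both are assumed over a range.

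| True DLT rate | m = 0 | m = 10% | m = 25% | m = 50% |
|---|---|---|---|---|
| 0.20 | 0.709 | 0.752 | 0.814 | 0.906 |
| 0.33 | 0.434 | 0.500 | 0.605 | 0.783 |
| 0.50 | 0.172 | 0.234 | 0.351 | 0.600 |

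The 82% figure becomes 78%, 71% and 55% at m = 10%, 25% and 50%.

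**The case against.** **The table may be damaged.** In the machine-read text other rows are plainly displaced: irinotecan lands under Days 2 and 15, and footnote p lands under Days 10, 17 or 22 in other rows. If the adverse-event row is moved so that its footnote p sits on Day 15, its next mark falls on Day 22, so Day 22 may be a safety contact. This stands as a caution. The CBC row itself fits its columns and footnotes, and an adverse-event contact yields no blood count.

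**A Day 17 count may be implied.** Section 10 wants all safety assessments done before any agent on dosing days, and Section 7.3 lists laboratory tests among them. That reading is fair, but the count would precede the second dose and would not cover the period after it.

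**The plan has a backstop.** A reader might infer that these DLTs cannot be observed at all. The documents do not support that. The window includes the Cycle 2 Day 1 assessments. A low ANC then fails the start-of-cycle criteria (7.2.2), the delay extends cycle 1 (5.1), and labs are repeated before treatment resumes (7.3). Grade 4 neutropenia on Day 15 likewise triggers a hold under Table 7.2.4. Febrile neutropenia would probably prompt an unscheduled count. What remains open is the episode that recovers before Cycle 2 Day 1, and the absence of any stated interval for repeat counts. Permission to test when clinically indicated does not reach a patient without symptoms.

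**Bias is not shown.** A reader might also infer that the MTD is biased upward by a known amount, for instance because 12 of 28 days (43%) lack a count. That is a share of calendar days, not of DLTs. The NSC dose is capped at level 4, and the RP2D also draws on the full toxicity profile. Only the direction is supported. It still bears on the recommended dose, because the MFD is defined as level 4 together with irinotecan schedule A.

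**Conclusion.** The point holds in a limited form. On Table 10 as read, a hematologic DLT that starts after the Day 17 dose and resolves before the Cycle 2 Day 1 labs is not seen by any scheduled count. For neutropenia this means early-onset episodes of about 8 to 11 days (up to 13 days at levels 1 and -1), and fewer if the labs are drawn early: only 8 to 9 days with a Day 27 count. Longer episodes are still present at the count. Separately, scheduled counts cannot by themselves establish a duration above 7 days.

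Hematologic DLTs may therefore be under-counted, which could only favour escalation or retention of the irinotecan schedule. The size is unknown, and the escalation probabilities above are illustrations under assumed rates and assumed missed shares. The conclusion rests on the Day 22 cell of the CBC row being truly blank. If a mark was lost there, the unseen-nadir problem shrinks but the duration problem remains.

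**What to change.** 1. Check the source version of Table 10 for a CBC mark on Day 22.
2. If there is none, add a cycle 1 CBC with ANC in the existing Day 22 column, with a local draw allowed as footnote c already provides.
3. In either case, state for DLT scoring that any grade 4 count in cycle 1 is followed by repeat counts close enough together to establish whether it lasts more than 7 days, and say how those days are counted. A Day 22 count alone is not enough.

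The cost is a calendar amendment, one routine draw per patient in cycle 1, and a few repeat draws in patients with grade 4 values. No dose or treatment rule changes.
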